1.2.2.2 Efficacy

Data from a 4-week treatment study in anemic CKD patients not on dialysis (Study [REDACTED]) showed that roxadustat promoted erythropoiesis at lower doses in CKD patients than in healthy subjects. In contrast to the classical paradigm suggesting that anemia

in CKD patients is caused by the inability of these patients to produce EPO, the results of this study suggest that the EPO production in this patient population is sufficient to achieve a robust erythropoiesis. With roxadustat 0.7 mg/kg TIW dosing, mean maximum Hb increased by 1.0 g/dL over a 6-week period in anemic CKD patients who completed 4 weeks of dosing; more robust mean Hb increases of 2.0 to 2.3 g/dL occurred at roxadustat doses of 1.5 and 2.0 mg/kg TIW, respectively. Hb responder (Hb increase of ≥ 1.0 g/dL) rates were 62%, 60%, 91%, and 100% in the roxadustat 0.7, 1.0, 1.5, and 2.0 mg/kg TIW cohorts, respectively. The Hb responses were also robust at the higher roxadustat doses (1.5 to 2.0 mg/kg) in the BIW dosing groups. With the additional criterion that Hb achieve a level of ≥ 11.0 g/dL as well as increasing by ≥ 1.0 g/dL, the Hb responder rate with roxadustat 2.0 mg/kg was 89% and 91% in BIW and TIW dosing, respectively. The rapid rates of rise in Hb with roxadustat treatment were not accompanied by elevations in blood pressure (BP), as has been reported with ESA treatment [Eschbach et al, 1989].

Data from a 16- to 24-week treatment study in CKD patients not on dialysis (Study FGCL-4592-041) showed absolute and weight-based doses of roxadustat, administered TIW and BIW, effectively corrected Hb levels in these patients. For cohorts that have completed treatment, corrected Hb levels were maintained within target range for the 16- or 24-week treatment period. The median time to Hb response was 28 days for subjects who received adequate weight-based or absolute starting doses of roxadustat and longer for those who received a lower absolute starting dose. Dose-response trends suggested that starting doses of 1.0–1.6 mg/kg roxadustat administered TIW are appropriate to correct Hb levels during 4 weeks of treatment in non-dialysis CKD patients. Dosing frequency reduction, once Hb correction is achieved, appears to be feasible to maintain Hb in the target range.

Data from a 6- and 19-week treatment study in ESRD patients on dialysis showed the feasibility of converting patients from a stable ESA dose to roxadustat (Study FGCL-4592-040). In the 6-week dose range portion of this conversion study (during which roxadustat doses were mostly fixed upon switching from stable doses of epoetin alfa), dose response was observed. The 1.0 mg/kg roxadustat dose was comparable to the epoetin alfa control, which had a small decline in Hb levels from BL and a lower percent Hb responder rate compared to the higher doses of roxadustat. The 1.5 and 2.0 mg/kg roxadustat dose arms resulted in a Hb increase of about 1 g/dL from BL and an 89% response rate, more than double that of the epoetin alfa arm, despite the absence of IV iron supplementation. Regression slope analyses of Hb values over time showed that the estimated rate of Hb rise was positive and statistically significant for the 1.5 and 2.0 mg/kg dose cohorts, with a Hb increase of 0.22 g/dL ($p=0.0040$) and 0.18 g/dL ($p=0.0146$) per week, respectively. In the 19-week portion of the study, during which dose-titration was allowed, Hb maintenance was demonstrated to be durable in roxadustat treatment arms (combined) over a 19-week period. For further information refer to the most recent version of the Investigator's brochure.

1.2.2.3 Summary

In summary, roxadustat is an orally active HIF-PH inhibitor with potent erythropoietic effects. Repeated intermittent dosing of roxadustat results in intermittent activation of HIF, intermittent induction of endogenous EPO and a dose-dependent erythropoiesis. The clinical data collected thus far suggest that roxadustat is generally safe and well tolerated in healthy adult subjects, and in dialysis and non-dialysis CKD patients with anemia who have been enrolled and treated in completed and ongoing clinical studies. Roxadustat leads to a robust dose-related erythropoietic response in patients with CKD-associated anemia. Roxadustat dosing induces a transient elevation in endogenous EPO level that is close to the physiologic range, but much lower than the plasma EPO level associated with IV ESA dosing, suggesting a coordinated erythropoiesis mechanism that is different from that of ESA therapy.

1.3 Summary of Key Safety Information for Study Drugs

The overall frequency and type of treatment-emergent adverse events (TEAEs) and serious adverse events (SAEs) observed in the clinical studies conducted with roxadustat reflect events that would be expected to occur in CKD patients. The most commonly reported adverse events (AEs) in healthy subjects were headache, pharyngolaryngeal pain, and nasal congestion. The most commonly reported AEs (> 5%) in CKD patients not on dialysis were diarrhea, nausea, urinary tract infection, nasopharyngitis, peripheral edema, hyperkalemia, headache, and hypertension. The most commonly reported AEs (> 3%) in CKD patients on dialysis were diarrhea, nausea, hypertension, and upper respiratory tract infection. The only expected non-serious adverse drug reaction is heart rate (HR) increase.

Safety analyses did not reveal any association between the rates of occurrence of cardiovascular events with roxadustat, or any effect on adverse event rates related to either increasing Hb levels or on the rate of change of Hb levels.

AEs commonly reported with ESA use have been reported at lower rates such as hypertension (1% in Study ██████████, and 6.9% in Study FGCL-4592-041) and thrombosis (overall incidence < 1 %). No increased cancer risk has been noted with roxadustat treatment. However, the study program was not powered to detect absence of cancer risk.

Liver enzymes were monitored closely throughout the phase 2 roxadustat clinical development program. Increases in liver enzymes were infrequently seen, and were generally mild and transient in nature. No case of Hy's Law was observed throughout the program. An independent data and safety monitoring committee concluded that there was no concern for hepatotoxicity with roxadustat.

A number of pancreatitis events were noted during the phase 2 roxadustat clinical development program, the majority of which have been associated with gallstones or biliary sludge; one of which was due to a pancreatic duct stricture, and another case had multiple risk factors for pancreatitis. Only 1 of the pancreatitis cases was considered as possibly related by the investigator. Amylase levels were routinely measured in the FGCL-4592-040

study and mean levels were not found to be elevated during the course of the study. A higher incidence of pancreatitis in patients with type 2 diabetes mellitus, and CKD, has been well described in the literature.

For further information refer to the most recent version of the Investigator's Brochure.

1.4 Risk-Benefit Assessment

Based upon the results of the studies described above the benefit of roxadustat is the correction of anemia and relief of signs and symptoms of anemia resulting in an increased QoL, improved physical functioning and performance. Treatment with roxadustat triggers a pharmacodynamic response which translates into correction of anemic Hb levels and maintenance of these corrected Hb levels.

Patients treated with placebo may be at risk of achieving insufficient efficacy as expressed by Hb levels not improving significantly or worsening as compared to BL. As a result they may have no improvement in QoL, impairment of physical functioning and performance.

An established dose adjustment algorithm, very similar to the one used in phase 2, will be used during the study to titrate roxadustat doses to enable patients to achieve and maintain Hb levels within target range, while allowing investigators to closely monitor the rate of rise of Hb levels. Roxadustat doses may be held and/or the use of therapeutic phlebotomy is allowed in the event of excessive hematopoiesis. In case of insufficient response to study drug (placebo or roxadustat) rules for the use of rescue medication/procedures such as IV iron, ESAs or red blood cell transfusion are in place in order to assure safety of the affected study subjects.

In pharmacokinetic studies there was no evidence of drug accumulation with the proposed clinical regimen of up to 3 times weekly dosing. The overall frequency and nature of AEs and SAEs observed in clinical studies thus far generally reflect events what would be expected to occur in the dialysis and non-dialysis CKD patient populations, and did not reveal any particular safety concern.

A drug interaction with statins is a potential risk. To mitigate this risk, recommendations for maximum statin doses are included in the study protocol. There is a potential risk that the drug interaction between phosphate-binders and roxadustat could decrease the efficacy of roxadustat, which will be mitigated by Hb-based dose adjustments. There is also a potential risk that a subject who suddenly discontinues or decreases the dose of a phosphate binder might be exposed to increased concentrations of roxadustat, although there are no data evaluating this potential effect. Although drug interaction of roxadustat with phosphate binders is an identified effect, it is unclear whether this interaction poses a true risk to subjects since the pharmacokinetics of discontinuing phosphate binder or changing the phosphate binder dose has not been investigated. Subjects who suddenly discontinue or decrease the dose of a phosphate-binder are advised to discuss changes in their use of phosphate binders with the investigator. As a further risk mitigation, this study protocol includes a recommendation that roxadustat be taken separately from a phosphate binder.

The safety of treatment with roxadustat and placebo in this study will be carefully monitored including AEs and serious adverse events (SAEs), and laboratory parameters including electrolytes, liver enzymes, and iron indices. Emphasis will be placed on cardiovascular and cerebrovascular events, which are not uncommon in the study population; an independent expert panel will assess and adjudicate all significant occurrences of such events. In addition, an independent Data Safety Monitoring Board (DSMB) will perform regular, periodic assessments of blinded and unblinded data to detect any potential safety signals that may arise during the study and advise the sponsor accordingly.

Based on the clinical and non-clinical experimental results to date, it can be expected that the orally administered roxadustat will be efficacious and safe in the treatment of anemia of CKD. The risk mitigation measures applied in this protocol are deemed to sufficiently assure that major risks for the patient can be avoided. The benefit-risk for the participation of patients in this study is therefore considered to be acceptable.

2 STUDY OBJECTIVE(S), DESIGN AND ENDPOINTS

2.1 Study Objectives

2.1.1 Primary Objective

The primary objective of this study is to evaluate the efficacy of roxadustat in the treatment of anemia in non-dialysis CKD subjects.

2.1.2 Secondary Objectives

The secondary objectives in this study are to:

- Evaluate the safety of roxadustat in the treatment of anemia in non-dialysis CKD subjects.
- Evaluate HRQoL benefit of roxadustat treatment in subjects with CKD anemia.
- Evaluate the need for anemia rescue therapy with roxadustat in subjects with CKD anemia: RBC transfusion, ESA, or IV iron.

2.2 Study Design and Dose Rationale

2.2.1 Study Design

2.2.1.1 General

This is a phase 3, multi-center, randomized, double-blind, placebo controlled study in anemic subjects with Stage 3, 4 or 5 CKD who are not on dialysis. This study is planned to recruit subjects from approximately 200 study centers, globally.

The study is planned to provide key efficacy and safety data for the approval of roxadustat in the treatment of anemia associated with CKD. Another study with similar design will be conducted by FibroGen Inc, in study centers across North America, Latin America and Asia Pacific.

2.2.1.2 Study Population

The study population consists of subjects with CKD stages 3, 4, and 5 (estimated glomerular filtration rate [eGFR] < 60 mL/min/1.73 m²) who are anemic and not receiving dialysis. Anemia is defined by mean Hb ≤ 10.0 g/dL upon repeated screening measurements. Subjects do not need to be iron replete at BL; inclusion is permitted if ferritin ≥ 30 ng/mL (≥ 67.4 pmol/L) and Transferrin Saturation (TSAT) ≥ 5%. Anemia of non-renal origin is to be excluded. Washout periods of at least 12 weeks for any prior ESA or IV iron treatment or at least 8 weeks for any RBC transfusion prior to randomization have been mandated in order to exclude a potential impact of these extraneous anemia treatments on the assessment of efficacy.

2.2.1.3 Description of Study

Subjects will take roxadustat or placebo orally as a combination of tablets of different strengths. All tablets for subjects receiving roxadustat will contain active ingredient whereas all tablets for subjects receiving placebo will contain just placebo. The study will consist of 3 study periods as follows:

- Screening period: up to 6 weeks.
- Treatment period: minimum 52 weeks (primary treatment period) up to a maximum of 104 weeks (extended treatment period) or until the last subject randomized to treatment has completed 40 weeks of treatment (or at the forecasted week 40 date if this subject discontinues treatment early). Treatment period for last patient randomized is 52 weeks.
- Post-treatment follow-up period: 4 weeks.

Refer to the study schema in [Figure 1](#).

Subjects that have discontinued treatment prior to their projected week 104 will continue to be followed for vital status and SAEs, cardiovascular and thromboembolic AEs in post study follow up.

2.2.1.3.1 Screening Period

During the screening period, subjects' eligibility for study participation will be assessed.

2.2.1.3.2 Treatment Period

After subjects have been confirmed eligible for study participation, they will be randomized to receive 1 of 2 treatment arms. The randomization will result in a 2:1 ratio of subjects receiving roxadustat or placebo, respectively.

The initial study drug dose (per dose amount) is based on a tiered, weight-based dosing scheme shown in [Table 2](#).

Table 2 Initial Study Drug (Roxadustat/ Placebo) Dosing

Study Drug (Dose Frequency)	Weight (≥ 45 to ≤ 70 kg)	Weight (> 70 to ≤ 160 kg)
Roxadustat/Placebo (TIW)	70 mg	100 mg

Study drug will be dosed initially for Hb correction, until subjects achieve central Hb value of ≥ 11.0 g/dL and Hb increase from BL of ≥ 1.0 g/dL at 2 consecutive study visits separated by at least 5 days (correction period).

Once Hb correction is reached the subject will enter the maintenance period. The aim of the maintenance period is to treat to a Hb level of 11.0 g/dL by maintaining the Hb levels between 10.0 g/dL and 12.0 g/dL. During the treatment period, subjects will attend weekly study visits from day 1 to week 2, followed by every other week study visits from weeks 4 to 24 and thereafter every 4 weeks until the end of treatment (EOT). Subjects will be treated with roxadustat or placebo for at least 52 weeks and will continue taking the double-blind treatment as they were assigned until a maximum of 104 weeks. Depending on the rate of recruitment, the maximum treatment period will be 104 weeks for subjects who were randomized early into the study.

- The last subject randomized will stop treatment at the minimum of 52 weeks.
- When the last subject randomized reaches 40 weeks of treatment (or the forecasted week 40 date, if the last subject randomized discontinues treatment early)
 - Subjects beyond 52 weeks treatment will stop treatment at this point.
 - Subjects that have not yet reached 52 weeks treatment will continue until they reach 52 weeks treatment.

For details on study drug dosing, see [Section 5.1].

2.2.1.3.3 Follow-up Period

After the Treatment period, subjects proceed to the 4-week post-treatment follow-up period.

2.2.1.3.4 Post-study Follow-up Period (Only for Subjects Prematurely Discontinued from Treatment)

Subjects that have stopped treatment prior to their projected week 104 will complete the EOT visits (EOT visit and EOT + 2 weeks visit) and the end of study (EOS) visit. Thereafter, these subjects will continue to be followed up on a 6-monthly frequency for vital status and SAEs, cardiovascular and thromboembolic AEs until their projected date of completion (i.e., projected week 108 date) or, if earlier, until the last subject randomized reaches EOS, or until consent withdrawn.

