Extended treatment period	Period of time that patient is treated from end of primary treatment period (52 weeks) up to 104 weeks
Hb response	
 • Hb \geq 11.0 g/dL and a Hb increase from baseline (BL) by \geq 1.0 g/dL in any subject with BL Hb > 8.0 g/dL, OR • an increase from BL by \geq 2.0 g/dL in any subject with BL Hb \leq 8.0 g/dL at 2 consecutive visits separated by at least 5 days during the first 24 weeks of treatment without rescue therapy (i.e., red blood cell [RBC] transfusion, erythropoiesis-stimulating agent (ESA), or IV iron) prior to Hb response.
Investigational period	Period of time where major interests of protocol objectives are observed, and where the test drug or placebo (sometimes without randomization) is usually given to a subject, and continues until the last assessment after completing administration of the test drug or placebo.
Post study follow-up	Period of time from end of study (EOS) visit to projected week 108 or until the last subject randomized reaches EOS, whichever comes first. This period is only applicable to subjects who prematurely discontinued treatment. These subjects will be followed up on a 6-monthly frequency for vital status, SAEs, cardiovascular and thromboembolic AEs.

Terms	Definition of terms
Primary treatment period	Period of time that subject is treated from first treatment up to 52 weeks
Randomization	Action to allocate a subject to the treatment group or treatment cohort. Subjects will be randomized to roxadustat or placebo at day 1.
Rescreening	Process of repeating screening. If a subject fails screening they may be re-screened once if deemed appropriate; all screening procedures will be repeated. Renal ultrasound only to be repeated if not within 12 weeks prior to randomization.
Rescreening failure	Subject who is rescreened, but did not fulfill protocol inclusion and/or exclusion criteria for a second time and failed to receive randomized treatment, or decided not to participate anymore (withdrew consent) prior to the treatment period.
Screening	1) Process for retrieving candidates for the study. 2) Process for checking the eligibility of subjects usually done during the “pre-investigational period”
Screening failure	Screened subject, but did not fulfill protocol inclusion and/or exclusion criteria and failed to receive randomized treatment, or decided not to participate anymore (withdrew consent) prior to the treatment period.

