Serious Adverse Event	An adverse event is considered “serious” if, in the view of either the investigator or sponsor, it results in any of the following outcomes: results in death, is life threatening, results in persistent or significant disability/incapacity or substantial disruption of the ability to conduct normal life functions, results in congenital anomaly, or birth defect, requires in-subject hospitalization or leads to prolongation of hospitalization, or a medically important event.
Study period	Period of time from first subject screened to end of the last scheduled visit of the last subject randomized
Subject	An individual who participates in a clinical trial, either as a recipient of the investigational product(s) or as a control.
Treatment Period	Period of time from first study drug intake until last study drug intake. Minimum 52 weeks to a maximum of 104 weeks or until the last subject randomized to treatment has completed 40 weeks of treatment (or at the forecasted week 40 date if this subject discontinues treatment early)
Variable	Any quantity that varies; any attribute, phenomenon or event that can have different qualitative or quantitative values.

IV. SYNOPSIS

Title of Study	A Phase 3, Randomized, Double-Blind, Placebo Controlled Study of the Efficacy and Safety of roxadustat for the Treatment of Anemia in Chronic Kidney Disease Patients not on Dialysis [ISN/Protocol 1571-CL-0608]
Planned Study Period	From 1Q2013 to 4Q2017
Study Objective(s)	
The primary objective of this study is to evaluate the efficacy of roxadustat in the treatment of anemia in non-dialysis Chronic Kidney Disease (CKD) subjects.
 
The secondary objectives in this study are to:
 
 • Evaluate the safety of roxadustat in the treatment of anemia in non-dialysis CKD subjects. • Evaluate health-related quality of life (HRQoL) benefit of treatment with roxadustat in subjects with CKD anemia. • Evaluate the need for anemia rescue therapy with roxadustat treatment in subjects with CKD anemia: red blood cell (RBC) transfusion, or erythropoiesis-stimulating agent (ESA), or IV iron.
Planned Total Number of Study Centers and Location	Approximately 200 centers globally

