
Pharmacodynamics
	
Pharmacodynamic data may be submitted to population pharmacodynamic (PPD) or population pharmacokinetic/pharmacodynamic (PPK/PD) modeling. When deemed necessary, data from this study may be combined with data from other studies. Results will be reported in a separate PPK/PD modeling report.

V. FLOW CHART AND SCHEDULE OF ASSESSMENTS

Figure 1 Flow Chart

[figure not shown]

Table 1 Schedule of Assessments

Study Period:	Screening			Treatment ^a				Follow-up			Unscheduled Visits	Post study Follow-up Every 6 months until projected wk 108
	Up to 6 Weeks			Day 1 ^b	Weekly (wks 1 to 2) ± 2 days	Every 2 Weeks (wks 4 to 24) ± 2 days	Every 4 Weeks (wks 28 to 100) ± 3 days	EOT (wk 104) ± 3 days	EOT + 2 wks ± 3 days	EOS (EOT + 4 wks) ± 3 days		
Visit / Week:	S1	S2	S3									
Written informed consent	X											
Randomization				X								
Eligibility criteria	X			X								
Demographics and medical history including tobacco use	X											
Weight	X			X		wks 12, 24	wks 36, 52, 76	X		X	O ^c	
Physical examination	X			X		wks 12 ^d , 24 ^d	wks 36 ^d , 52 ^d , 76 ^d	X		X ^c	O ^{c, d}	
Blood pressure ^e , heart rate ^e , respiratory rate ^g	X	X	X	X	X	X	X	X		X	O ^c	
CBC with WBC differential, red cell indices and platelet count	X			X	X	wks 4, 8, 12, 20	wk 28 and every following 8 wks	X		X	O ^c	
Reticulocyte count, Hemoglobin content of reticulocytes (CHR)	X			X	X	wks 4, 6, 8, 12, 16, 20	wk 28 and every following 8 wks	X		X	O ^c	
Hemoglobin ^h		X	X			X	X		X		O ^c	
HemoCue® assessment ⁱ				X	X	X	X				O ^c	
Serum chemistry (incl LFT)	X			X		wks 4, 8, 12, 20	wk 28 and every following 8 wks	X	X	X	O ^c	
LFTs ^j					wk 2	wks 6, 16					O ^c	
Serum Lipid panel (fasting whenever possible)	X			X		wks 4, 8, 12, 20	wks 28, 36, 44, 52, 68, 84	X		X	O ^c	
Serum iron, ferritin, TIBC, TSAT	X			X		wks 4, 8, 12, 20	wk 28 and every following 8 wks	X		X	O ^c	
HbA1c	X			X		wk 12	wks 28, 36, 44, 60, 84	X		X	O ^c	
Vitamin B ₁₂ , folate	X											
HIV Immunoassay, HBsAg, anti-HCV antibody	X											

Table continued on next page

Study Period: Visit / Week:	Screening			Treatment ^a				Follow-up			Unscheduled Visits	Post study Follow-up
	Up to 6 Weeks	Day 1 ^b	Weekly (wks 1 to 2) ± 2 days	Every 2 Weeks (wks 4 to 24) ± 2 days	Every 4 Weeks (wks 28 to 100) ± 3 days	EOT (wk 104) ± 3 days	EOT + 2 wks ± 3 days	EOS (EOT + 4 wks) ± 3 days	Every 6 months until projected wk 108			
S1	S2									S3		

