The study period during which all AEs and SAEs must be reported begins after informed consent is obtained and ends 28 days after the last dose of study drug or through to EOS, except for pregnancy reporting [see Section 5.5.8]. For subjects that continue into the post study follow-up period, SAEs, cardiovascular and thromboembolic AEs will be captured until their projected date of completion of the follow-up period (i.e., projected week 108) or until the last subject randomized reaches EOS, whichever comes first.

During the AE reporting period, study site personnel will query each subject at each visit to actively solicit any AE occurring since the previous visit. All AEs will be collected in response to a general question about the subject's well-being and any possible changes from the BL or previous visit, but shall not be specifically solicited. There will be no directed questioning for any specific AE. This does not preclude the site from collecting and recording any AEs reported by the subject to site personnel at any other time.

Whenever possible, diagnoses should be recorded when signs and symptoms are due to a common etiology, as determined by qualified medical study staff. New indications for medications started after informed consent until 28 days after the last dose of study drug or through to EOS visit, will be recorded as AEs; recurrence or worsening of medical history problems requiring new or changes in concomitant medication, will also be recorded as AEs. Abnormal, clinically significant laboratory results, physical examination findings, and ECGs will be recorded as AEs if they are deemed by the investigator to meet criteria.

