6.2.1.3 Time to occurrence of a TEAE (by type of AE group)

TEAEs are also classified into a number of groups depending on the following factors:

- Serious TEAEs
- Death during the Safety Emergent Period
- Any deaths (during the 24-month period)
- Related Serious TEAEs
- TEAEs Leading to permanent Discontinuation of the study drug
- TEAEs NCI CTC Grade 3 or Higher
- MedDRA System Organ Class (SOC)

The time to occurrence for a subject with a TEAE for a given type (except any deaths) will be calculated (in years) as:

$(\text{First TEAE date of the given type during the Safety Emergent Period} - \text{Analysis date of first dose intake} + 1) / 365.25$

With 'Analysis date of first dose intake' defined in Section [6.5.4](#) All adverse events collected during the Safety Emergent Period will be counted as TEAE, irrespective of use of rescue therapy.

Subjects who have not experienced a TEAE for that given type will be censored; the subject will be censored and the time to censoring for these subjects will be calculated (in years) as:

$(\text{Date of End of Safety Emergent Period} - \text{Analysis date of first dose intake} + 1) / 365.25$

With date of end of Safety Emergent Period defined in Section [7.11.5](#)

For any deaths during the 24-month period (including those occurring during the Post-Study Follow Up Period), time to occurrence for a subject who died during study / post study follow up) will be calculated (in years) as:

$[\text{End date for corresponding Fatal AE} - \text{Analysis date of first dose intake} + 1] / 365.25$

With 'End date for corresponding Fatal AE' which cover both study and post-study FU occurring up to Day 760 (i.e., month 24 + one month follow up + 3 days window as per protocol).

Subjects who have not died; the subject will be censored and the time to censoring for these subjects will be calculated (in years) as:

$\text{Minimum between } [\text{Day 760 and Max (Date of last known date when subject alive (End of Post-study FU), Date of last contact (Post study FU visit/call), Date of last Study evaluation (EOS form))} - \text{Analysis date of first dose intake} + 1] / 365.25$

Additional analyses censoring data post dialysis:

Time to occurrence with censoring all data at the initiation of permanent dialysis will be calculated as above where events occurring after initiation of dialysis will not be considered.

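### Post-study follow-up of discontinued subjects ends at the last randomized subject's EOS with no forecast-date fallback, so that one subject's early exit could shorten it by up to 52 weeks

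*Protocol*

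**What the plan says.** Two study-wide stops depend on the last randomized subject.

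- **Treatment stop** (Protocol 2.2.1.3.2). Subjects beyond 52 weeks stop when the last randomized subject reaches 40 weeks of treatment, "or the forecasted week 40 date, if the last subject randomized discontinues treatment early". Subjects not yet at 52 weeks continue to 52. For the last subject, "The last subject randomized will stop treatment at the minimum of 52 weeks".
- **Post-study follow-up stop** (Protocol 2.2.1.3.4). Subjects who stopped treatment early complete EOT, EOT + 2 weeks and EOS. They are then contacted every six months "until their projected date of completion (i.e., projected week 108 date) or, if earlier, until the last subject randomized reaches EOS"; withdrawal of consent also ends the contacts. The key-terms definition is the same: "Period of time from end of study (EOS) visit to projected week 108 or until the last subject randomized reaches EOS, whichever comes first". Protocol 5.5.1 collects events in this period "until the last subject randomized reaches EOS, whichever comes first". The rule recurs in the synopsis, Table 1 footnote a, 3.3, 5.1.5 and 5.3.3.2, and in the SAP (key terms, Table 1 footnote a, 3.2.3). None of these places gives a forecast date.

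The schedule of assessments places the EOS visit relative to actual EOT: "EOS (EOT + 4 wks) ± 3 days".

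The SAP uses the follow-up in its any-death analysis, which counts deaths up to Day 760 (SAP 6.2.1.3: "For any deaths during the 24-month period (including those occurring during the Post-Study Follow Up Period"). Survivors are censored at the earlier of Day 760 and their last known contact.

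**The concern.** The sponsor foresaw that the last randomized subject might discontinue and protected the treatment stop against it. The follow-up stop, tied to the same person, lacks that protection. Because EOS moves with actual EOT, an early exit by that subject brings the trigger forward for every discontinued subject still being followed. Anyone who discontinues after the trigger would have no post-study follow-up at all.

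Subjects still on study drug would carry on to the forecast Week 40 date or their own Week 52, with adverse events collected at visits until their own EOS. Follow-up for death would therefore be shortened for discontinued subjects only. The SAP allows that discontinuation may differ by arm (7.5.1.4 and Appendix 7), so the cut could fall unevenly. The inverse-probability-of-censoring sensitivity list in SAP 7.5.1.4 covers deaths in the Safety Emergent Period but not any death. Vital status and events that are not collected during the trial may not be recoverable later.

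**Working it through.** **Inputs.** Maximum treatment is 104 weeks; the last subject's planned treatment is 52 weeks (Protocol 2.2.1.3.2). EOS is EOT + 4 weeks, ± 3 days (Protocol Table 1). Contacts are every six months, about 26 weeks. The planned study period is "From 1Q2013 to 4Q2017" (Protocol synopsis).

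**The plan's own figure.** 104 + 4 = 108, which reproduces the projected Week 108.

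**Loss at the study level.** Count weeks from the last subject's randomization.

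- Planned EOS of the last subject: 52 + 4 = week 56.
- If that subject stops at week t and attends EOS, the trigger falls at week t + 4.
- Shortfall: 56 − (t + 4) = 52 − t weeks.
- Results: t=0 gives 52; t=4 gives 48; t=12 gives 40; t=26 gives 26; t=40 gives 12; t=52 gives 0.
- Largest loss in contacts: 52 / 26 = 2.

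**Loss for one discontinued subject randomized r weeks before the last.** That subject's own Week 108 falls at week 108 − r on this scale. The loss is min(108 − r, 56) − min(108 − r, t + 4).

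- t=4: 48 weeks for r up to 52; 44 at r=56; 22 at r=78; 0 from r=100.
- t=0: 52 weeks for r up to 52; 48 at r=56; 26 at r=78; 0 from r=104.

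The full loss thus applies only to subjects randomized within 52 weeks of the last, and then tapers. These are upper limits: someone who enters post-study follow-up after the trigger loses only the part still ahead.

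**Share of subjects whose Week 108 falls after the stop.** The documents give no accrual curve. Assume uniform accrual over A weeks, with A = 260 (five years) − 6 (screening) − 56 (last subject to EOS) = 198. The share is (108 − EOS week of the last subject) / A.

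- Planned, EOS week 56: 52 / 198 = 26%.
- EOS week 8 (t=4): 100 / 198 = 51%.
- EOS week 8 with A = 210 or 150: 100 / 210 = 48%, 100 / 150 = 67%.

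These are shares of all randomized subjects. Only the discontinued fraction can lose data, and the documents state no discontinuation rate.

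**With a fallback to the forecasted week 56 date.** The stop no longer depends on t, and the shortfall is 0 weeks.

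**The case against.** The strongest reply is that the literal reading cannot be what was meant. Protocol 2.2.1.3.4 sends every early discontinuer into follow-up after EOS; read literally, the last subject's own EOS would both open and close that subject's follow-up. The key term for the study period runs to the last scheduled visit of the last randomized subject, and 5.3.3.2 treats a subject's own EOS as a projected date. Sites might therefore apply the planned date. That reading is plausible, but none of these places amends the rule. The rule's own sentence says projected for the subject's Week 108 and not for the last subject's EOS.

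The harm is also conditional: one particular subject must stop early and complete EOS. If that subject dies or is lost without an EOS visit, the trigger never fires on a literal reading, and others run to their own Week 108. That is not a premature stop, but it leaves the rule undefined.

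Some stronger inferences are tempting and are not supported:

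- *That follow-up stops for everyone.* It stops only for discontinued subjects short of their own Week 108.
- *That about half the trial loses data.* The 48–67% counts all randomized subjects, not discontinued ones.
- *That discontinued subjects are known to be at higher risk, or that the SAP expects discontinuation to differ by arm.* The documents do not establish the first, and the SAP calls the second only possible.
- *That the pooled MACE/MACE+ result is compromised.* This study contributes events to it, but its plan is separate, so whether it uses post-study events cannot be checked.

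**Conclusion.** The gap is real and modest. As written, the end of post-study follow-up depends on when one subject leaves, with a loss of up to 52 − t weeks (maximum 52, about two contacts) for subjects in, or later entering, that follow-up whose own Week 108 has not passed.

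The loss in weeks follows from the documents' own timings and assumes that the last subject completes EOS and that sites apply the rule literally. The shares rest further on the uniform-accrual assumption.

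Both primary endpoints are unaffected: every subject can still be treated to Week 52, and neither endpoint uses post-study data. Safety analyses limited to 28 or 7 days after last dose are also unaffected. In this study the exposure is in the any-death analysis to Day 760 and the descriptive summaries of post-study events. In the any-death analysis the result would be earlier censoring of discontinued subjects, not an error of derivation. The point merits correction because the remedy is cheap and the lost follow-up may not be recoverable.

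**What to change.** Wherever the rule ends follow-up at the last randomized subject's EOS, add: *(or the forecasted Week 56 date of that subject, if that subject discontinues treatment early or has no EOS visit)*. The places are:

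- Protocol: key terms, synopsis, Table 1 footnote a, 2.2.1.3.4, 3.3, 5.1.5, 5.3.3.2 and 5.5.1.
- SAP: key terms, Table 1 footnote a and 3.2.3.

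This matches the protection already given to the treatment stop and settles the case with no EOS visit. The cost is one repeated clause and at most about two further 6-monthly contacts per affected discontinued subject, which the design already intends when the last subject completes treatment.
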